1. STUDY PROTOCOL

1.1 Objectives

This study was designed to evaluate the safety and efficacy of the Soniflow System for the treatment of nasal congestion.

1.2 Study Design

This study is a prospective, single-center, interventional cohort study of acoustic resonance therapy (ART) for the treatment of nasal congestion using the Soniflow System. Subjects with nasal congestion as determined by the Total Nasal Symptom Score (TNSS) were consented and screened for study eligibility (score of 2 or 3 on the nasal congestion subdomain). Eligible subjects who consented to the study were mailed the device as well as provided a link to download the associated smartphone app. Subjects self-performed the treatment without assistance from the staff after reading the included instructions. The intervention consisted of two sequential 10-minute treatment sessions, with treatment time automatically tracked by the app. Subjects reported their baseline TNSS, including subscores for each of the 4 subdomains, prior to any intervention and immediately after each of the two 10-minute treatment sessions. In order to assess whether use of the product led to pain or discomfort, visual analog scales (VAS) for headache and facial pain were assessed at baseline and after each treatment session, with higher scores indicating increased symptom burden.

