1.3 Study Endpoints

Safety and efficacy were evaluated by the following primary and secondary endpoints.

Primary Endpoints

- Safety as evidence by an assessment of serious acute serious adverse events potentially associated with device
- Effectiveness as defined by improvement in nasal symptoms using the TNSS after one 10 minute treatment
- Use-ability for self-treatment

Secondary Endpoints

- Visual Analog Scale (VAS) for Headache
- Visual Analog Scale (VAS) for Facial Pain
- Percent of subjects requiring additional treatment and their subsequent change in TNSS

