2. STATISTICAL PLAN

Descriptive statistics and graphical summaries were used to summarize the data. For categorical variables, counts and percentages were calculated. For continuous variables, means, standard deviations or standard error were calculated. Changes in symptom scores and nasal congestion from baseline were evaluated using a paired t-test examining the distribution of within-patient changes from baseline to each of the two post-treatment intervals. A clinically meaningful change in TNSS from baseline was defined as the minimal clinically important difference (MCID) identified using anchor-based methods in allergic rhinitis, with a value of 0.28.

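### The headache and facial-pain VAS are meant to detect harm, but no planned analysis counts the subjects whose pain rose

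*Combined protocol and SAP*

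**What the plan says.** Section 1.2 (Study Design) gives the two scales a safety purpose: they were collected "In order to assess whether use of the product led to pain or discomfort". They "were assessed at baseline and after each treatment session, with higher scores indicating increased symptom burden", so a change can be computed for every subject after each of the two sessions.

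Section 1.3 (Study Endpoints) lists "Visual Analog Scale (VAS) for Headache" and "Visual Analog Scale (VAS) for Facial Pain" as secondary endpoints by name only, with no summary measure and no threshold. The primary safety endpoint is an "assessment of serious acute serious adverse events potentially associated with device".

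Section 2 (Statistical Plan) does not mention the VAS. Two statements could apply to them: "For continuous variables, means, standard deviations or standard error were calculated", and "Changes in symptom scores and nasal congestion from baseline were evaluated using a paired t-test examining the distribution of within-patient changes". The section also promises graphical summaries, without saying of what, and counts and percentages for categorical variables. Its one threshold for a meaningful change, 0.28, is for TNSS.

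**The concern.** Whether a device causes pain is a question about individual users: did some of them get worse, and how many? A paired t-test answers a different question, whether the average change differs from zero. If mild pain eases in most subjects and rises sharply in a few, the average can be flat or favourable. A small harmed share can also be too diluted to move the average detectably.

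Nothing else in the plan fills the gap. Non-serious headache or facial pain falls outside the adverse-event endpoint, so the VAS are the only stated measure of it, in a study whose objective includes safety. A report that followed the plan exactly could say that pain did not rise, or that it fell, and the reader could not tell how many users had clearly more pain after treatment.

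**Working it through.** **What the text commits to.** The plan states no sample size, power, VAS range or VAS SD, so it has no figure to reproduce. Against the harm question:

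- Mean with SD or SE: gives neither the direction nor the number of individual changes, and SE may replace SD.
- Paired t-test: tests the mean change only, although Section 2 describes it as examining the distribution of changes. That it covers the VAS at all is an inference from the term symptom scores. If it does not, only generic descriptive summaries remain and the gap is wider.
- Plots: no plot of individual VAS changes is specified.
- Counts and percentages: for categorical variables, and no VAS worsening category is defined.
- Adverse events: serious events only.

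**A hand example (assumed 0-10 scale, n = 40).** Six subjects rise by 2 and 34 fall by 0.5.

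- Mean change = (6 × 2 − 34 × 0.5)/40 = (12 − 17)/40 = −0.125
- SD = √[(6 × 2.125² + 34 × 0.375²)/39] = √(31.875/39) = 0.90
- t = −0.125/(0.904/√40) = −0.87, two-sided p = 0.39
- Count: 6/40 = 15% worsened, exact 95% CI 5.7% to 29.8%

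The planned test shows a small favourable mean and no signal. The count shows about one subject in seven with more pain.

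**Range of cases (all inputs assumed).** On a 0-100 VAS, a share *p* of subjects changes by +30 (SD 10) and the rest by −*d* (SD 8). The test is a two-sided 5% paired t-test, with 40,000 simulated studies per cell. The expected mean change is 30*p* − (1 − *p*)*d*; for *p* = 0.15 and *d* = 3 it is 4.5 − 2.55 = +1.95.

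| Harmed share | d | Expected mean change | Chance the test signals worsening, n = 30 / 50 / 100 |
|---|---|---|---|
| 15% | 0 | +4.5 | 39 / 65 / 94% |
| 15% | 3 | +1.95 | 6 / 11 / 24% |
| 15% | 6 | −0.6 | about 0.6% at each n |
| 10% | 0 | +3.0 | 21 / 38 / 70% |
| 10% | 3 | +0.3 | 1.4 / 2.0 / 2.8% |
| 10% | 6 | −2.4 | under 0.1% |
| 5% | 0 | +1.5 | 8 / 14 / 28% |
| 5% | 3 | −1.35 | 0.1% or less |
| 5% | 6 | −4.2 | 0% |

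With 5% harmed, the test declares significant *improvement* in 16/19/27% of studies at *d* = 3 and in 54/71/93% at *d* = 6.

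**Would the SD reveal it?** At *p* = 0.15, *d* = 6 the variance is 0.15 × 100 + 0.85 × 64 + 0.15 × 0.85 × 36² = 234.6, so SD = 15.3 against 8 in the unharmed. A reader might notice a large SD but could not tell which way the outlying subjects moved, or how many there were.

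**Would a count work better?** At *p* = 0.15, a cut of 20 points (illustrative, not a proposal) flags 84% of the harmed and 0.6% or fewer of the rest. About 13% of all subjects are flagged, and 96% or more of those are truly harmed. Counting any rise flags 57% of subjects at *d* = 0 and 34% at *d* = 6, of whom only 26% to 44% are harmed. The threshold therefore has to exceed measurement noise.

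**The case against.** The strongest reply is that this is an omission in a one-paragraph plan, not an error. Plots and descriptive summaries are promised, nothing forbids showing individual VAS changes, and a paired t-test on a VAS is conventional. That is fair, but the plan does not commit to any display or count that answers the harm question.

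The illustration is also open to challenge. Every input is assumed. In four of the nine cells the expected mean is clearly unfavourable (+4.5, +1.95, +3.0, +1.5). There the mean itself would on average show a rise, and a non-significant result reflects low power, not masking. Strong masking needs an improving majority, yet entry requires congestion, not pain. Subjects who start near zero cannot fall by 6 points, and the normal model ignores that floor. If low baseline pain also makes the rest less variable (assumed SD 2, *d* = 0), detection rises to about 53/88/99.9% with 15% harmed and 24/60/96% with 10% harmed at n = 30/50/100. With 5% harmed it is still only 5/17/56%. All of this stands. It limits how likely masking is, but does not remove the possibility, and the documents give no baseline pain data to decide between the scenarios. Even where the test detects a rise, it does not say how many subjects were affected.

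Finally, the documents offer no VAS threshold, and the plan is written in the past tense, so a cut-off chosen now may be post hoc. That also stands. It can be handled by labelling, and a plot of every subject's change needs no cut-off.

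**Conclusion.** The concern holds. The VAS have a stated harm purpose, and no stated analysis reports how many subjects had more pain after use. The planned mean-level summaries can be flat or favourable over a harmed minority.

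The size is a matter of possibility, because N, scale, SDs, harmed share and offset are all assumed. In the illustration the chance of signalling worsening runs from 94% (15% harmed, nobody else improves, n = 100) down to zero (5% harmed, the rest improve by 6). The gap concerns secondary endpoints and does not affect the TNSS effectiveness analysis. It should be corrected because the safety statement on non-serious pain depends on it. Confidence is medium, given the unknown N and the inference that the VAS fall under symptom scores.

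**What to change.** For each VAS and each session, report the number and percent of subjects whose score rose from baseline by at least a pre-stated amount larger than measurement noise, with an exact (Clopper-Pearson) 95% CI. Show the distribution of individual changes, for example a plot of each subject's change. If data have already been seen, label the threshold and the count as post hoc.

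Name the VAS in Section 2, keep the mean change as descriptive, and state that a non-significant t-test will not be read as evidence of no pain. Because this is a "prospective, single-center, interventional cohort study" with no comparator described, add that the count describes worsening after use and does not prove that the device caused it.

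The cost is one table and one plot from data already collected. The safety statement may become less favourable, and intervals will be wide in a small study: 4/30 gives 3.8% to 30.7%, 7/50 gives 5.8% to 26.7%, and 13/100 gives 7.1% to 21.2%.

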1.3 Study Endpoints

Safety and efficacy were evaluated by the following primary and secondary endpoints.

Primary Endpoints

- Safety as evidence by an assessment of serious acute serious adverse events potentially associated with device
- Effectiveness as defined by improvement in nasal symptoms using the TNSS after one 10 minute treatment
- Use-ability for self-treatment

Secondary Endpoints

- Visual Analog Scale (VAS) for Headache
- Visual Analog Scale (VAS) for Facial Pain
- Percent of subjects requiring additional treatment and their subsequent change in TNSS

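### The primary safety endpoint is limited to serious, acute, potentially device-associated events, with no collection method, window or confidence limit described, so a count of zero would be weak evidence of safety

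*Combined protocol and SAP*

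**What the plan says.** Section 1.1 makes safety one of the two aims of the study. Section 1.3 lists as its first primary endpoint "Safety as evidence by an assessment of serious acute serious adverse events potentially associated with device". It does not say who decides on the association, by what criteria, or over what period.

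Section 1.2 describes the conduct of the study. "Eligible subjects who consented to the study were mailed the device", and "Subjects self-performed the treatment without assistance from the staff after reading the included instructions". On exposure: "The intervention consisted of two sequential 10-minute treatment sessions, with treatment time automatically tracked by the app". The TNSS was reported before treatment and "immediately after each of the two 10-minute treatment sessions"; in addition, "visual analog scales (VAS) for headache and facial pain were assessed at baseline and after each treatment session". The stated purpose of those scales is to detect pain or discomfort caused by the product, and section 1.3 lists both as secondary endpoints. No other assessment, no adverse-event question and no later contact is described. No comparator arm is described either.

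For the analysis of an event count, section 2 offers only this: "For categorical variables, counts and percentages were calculated". No interval for a proportion, no acceptance criterion and no sample size appears anywhere.

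**The concern.** Each of the three conditions in the endpoint can remove events from the count and none can add any. The non-serious events that a 20-minute exposure might plausibly cause fall outside the primary endpoint by its wording. The described assessments are a nasal symptom score and two pain scales, and none of these is an instrument for recording a serious adverse event. The plan therefore does not show where data for its first primary endpoint come from, or for how long a subject is observed.

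The likely summary is a line such as 0 (0%). Without an interval, an observation window or a statement of how events were sought, a reader may take that line as a demonstration of safety. What is at stake is whether the study can support the safety half of its objective.

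**Working it through.** **What can reach the safety result, going by the described procedures**

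| Type of event | Primary safety endpoint | Other described route |
|---|---|---|
| Serious, acute, potentially associated | Eligible, but collection method and window not described | None described |
| Serious, but not acute or not potentially associated | Not eligible | None described |
| Non-serious headache or facial pain, up to the score after session 2 | Not eligible | VAS, secondary endpoint |
| Other non-serious adverse event | Not eligible | None described as a safety measure |
| Non-serious event starting after the last score | Not eligible | None described |

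**What a count of zero would mean**

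The documents give no sample size, expected event rate or safety margin, so there is no figure of the plan's to reproduce. The values of n and of the true rate p below are assumptions. All results take every eligible event to be captured.

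- Exact two-sided 95% upper limit after 0 events in n subjects: U = 1 − 0.025^(1/n).
- Chance of observing zero events at true rate p: (1 − p)^n.

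| Assumed n | U after 0/n | P(zero) at p = 0.1% | P(zero) at p = 1% | P(zero) at p = 5% |
|---|---|---|---|---|
| 20 | 16.8% | 98.0% | 81.8% | 35.8% |
| 50 | 7.1% | 95.1% | 60.5% | 7.7% |
| 100 | 3.6% | 90.5% | 36.6% | 0.6% |
| 200 | 1.8% | 81.9% | 13.4% | about 0% |

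For example, with n = 50, U = 1 − 0.025^(1/50) = 0.0711, and P(zero) at 1% is 0.99^50 = 0.605.

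The smallest n at which zero events excludes a rate p, at a one-sided 95% level, is ln 0.05 / ln(1 − p), rounded up: 59 subjects for 5%, 299 for 1% and 2,995 for 0.1%.

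**Effect of incomplete capture**

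If only a fraction c of eligible events is recorded, independently of one another, the recorded rate is c × p, and the upper limit for the true rate becomes U / c. The documents give no basis for a value of c. Since c cannot exceed 1, the limits in the table are the most favourable ones.

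**The case against.** The strongest reply is that much of the criticism rests on silence. Four stronger readings are tempting, and the documents do not support them.

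- *Data collection stops when session 2 stops.* Section 1.2 times the last described scores. It does not set an end to adverse-event collection, and section 1.3 does name an assessment of events. What can be said is that the method and window are not described.
- *An unblinded assessor filters events out.* The endpoint says potentially associated, which is an inclusive test, and no assessor or adjudication step is described. It remains a relatedness condition, but how strictly it was applied is unknown.
- *Subjects were alone at home.* This is a reasonable inference from a mailed device and unassisted self-treatment, but it is not stated.
- *A zero count is virtually guaranteed.* That depends on assumed values. At a 1% rate the chance of zero is 36.6% with 100 subjects and 13.4% with 200. Zero is the likely result only for rare events or small samples.

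Two further points stand in part. The headache and facial pain scales are the protocol's own measure of non-serious discomfort, so such harm is not ignored; the gap is other symptoms and later events. And the binomial figures describe sample size and rarity, not the loss from the narrow definition or the missing window. They would be the same for serious events under a broader endpoint. They show why an interval is needed; they do not measure under-capture.

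The objection does not remove the core. The restriction to serious, acute, potentially associated events is written into the endpoint, and the analysis section plans no interval.

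**Conclusion.** The concern holds in this form: a zero count, reported as the plan describes, would be weak evidence for the safety objective. Three features of the text combine to make it so: a narrow primary definition, no described method or window for ascertaining events, and no confidence limit.

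The size can be given only conditionally. Under full capture, zero events would be compatible with a true rate of up to 16.8%, 7.1% or 3.6% for 20, 50 or 100 subjects, and those sample sizes are assumed. Any under-capture makes the limits worse by an unknown amount. The documents do not show that events were missed, or that the device is unsafe. The point should be addressed before a safety conclusion is drawn; it does not bear on the efficacy analysis.

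**What to change.** **If collection can still be changed**

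- Record all adverse events of any severity, regardless of judged relatedness, from the start of session 1 to a fixed later time such as the next day.
- Ask one standard question after each session, and send one follow-up message to every subject who started session 1. Section 1.2 says only that the app tracks treatment time, so use the app if it can send messages and email or text otherwise.
- Report the proportions with any event and with a serious event, each with an exact 95% confidence interval. Show potentially device-associated events as a labelled subset, and say who classified them. State how many subjects did not respond.

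**If collection is already complete**, as the past tense of the documents suggests it may be: report the exact upper limits beside the counts, state how and for how long events were ascertained, and confine the safety conclusion to that.

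**Cost.** New endpoint wording, one question and one message per subject; no visit is needed. More minor, unrelated events will be listed, and without a control arm they cannot be separated from background symptoms. Some subjects will not answer the follow-up. For completed data the cost is a few lines of reporting.

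### Does a study of nasal congestion need the congestion subscore as a named primary endpoint beside the TNSS?

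*Combined protocol and SAP*

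**What the plan says.** The aim in section 1.1 is to "evaluate the safety and efficacy of the Soniflow System for the treatment of nasal congestion". Section 1.2 sets its entry score on one item only: subjects were "screened for study eligibility (score of 2 or 3 on the nasal congestion subdomain". It states no minimum for the other three items.

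Section 1.3 opens with "Safety and efficacy were evaluated by the following primary and secondary endpoints". The primary effectiveness entry is "Effectiveness as defined by improvement in nasal symptoms using the TNSS after one 10 minute treatment". The one secondary entry on nasal symptoms is "Percent of subjects requiring additional treatment and their subsequent change in TNSS". The congestion subscore appears in neither list.

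It does appear elsewhere. Under section 1.2 the TNSS was reported "including subscores for each of the 4 subdomains, prior to any intervention and immediately after each of the two 10-minute treatment sessions". Section 2 then states: "Changes in symptom scores and nasal congestion from baseline were evaluated using a paired t-test", applied from baseline to each of the two post-treatment times. The value 0.28 for a clinically meaningful change is defined for the TNSS. The plan does not say whether the congestion test is primary, secondary or supportive.

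**The concern.** The question asked and the endpoint that answers it do not quite match. The study asks about congestion and recruits on congestion, but judges effectiveness on a score that also covers three other symptoms. The natural reading of the primary endpoint is the total score, since section 2 mentions nasal congestion separately from symptom scores.

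A total can improve through the other items while congestion stays where it was. A positive TNSS result could then be presented as evidence of an effect on congestion. Because the planned congestion test has no stated status, its result could be stressed or played down once it is known. At stake is whether the effectiveness conclusion speaks to the symptom in the study's stated aim.

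**Working it through.** The plan gives no sample size, power or significance level on this point, so there is no figure of its own to reproduce. The check has three parts.

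**1. What is analysed now, and what would be analysed after a change**

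| Element | Plan as written | Congestion raised to primary |
|---|---|---|
| Congestion subscore at baseline and after each session | Yes (section 1.2) | Same |
| Paired t-test of TNSS change at both times | Yes (section 2) | Same |
| Paired t-test of congestion change at both times | Yes (section 2) | Same |
| Status of the congestion test | Not stated | Stated |

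Three of the four rows do not move. The difference is a label.

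**2. Can the TNSS reach 0.28 with no change in congestion?**

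The input is 0.28 from section 2. The documents do not say whether the TNSS is the sum or the mean of its four items, so both are shown. Let congestion change by 0 and let each of the other three items fall by a mean of *d*.

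- Sum: 3*d* = 0.28, so *d* = 0.28 / 3 = 0.093. In total this is 0.28 item points per subject, or 28 one-point falls per 100 subjects.
- Mean: 3*d* / 4 = 0.28, so *d* = 4 × 0.28 / 3 = 0.373. In total this is 4 × 0.28 = 1.12 item points per subject, or 112 one-point falls per 100 subjects.

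The other three items together must therefore average at least 0.28 points (sum) or 1.12 points (mean) at baseline. If items run from 0 to 3, which is an assumption, their joint maximum is 9, and these are 0.28 / 9 = 3.1% and 1.12 / 9 = 12.4% of it.

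So the case can arise. The arithmetic gives no probability for it. Congestion is the one item that every subject must score at 2 or 3 on screening, so it has room to fall in everyone, whereas the other items have no required minimum. If they were all 0 at baseline, the TNSS could improve only through congestion. Where the case did arise, the planned congestion test would show it.

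**3. What primary status would do to error rates**

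Assume a two-sided 95% confidence interval for each measure after the first session, hence 2.5% in the direction of improvement. The plan states no level.

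- Each measure supports its own claim: the chance of at least one false claim is at most 2 × 2.5% = 5%.
- Both must succeed for any claim: the chance of a false claim when either effect is absent is at most 2.5%, but a gain on the TNSS alone would then support nothing.

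These are different rules with different costs, and neither is plainly better than the present arrangement. Nor does either address regression to the mean. Subjects enter with a high congestion score and there is no control arm, so a confidence interval excluding zero could arise partly from that source. How far depends on whether the screening score also serves as baseline, which is not stated.

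**The case for a change.** The strongest case for a change is that the study's main question has no designated endpoint, the data are already collected, and a few sentences would settle the matter. A planned test without a status leaves room to choose its weight after the results are known. If the wording of the primary endpoint could mean either the total or the subscore, then the primary measure is itself loose.

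Part of this stands. Section 1.3 does not say total score, and nothing ties the congestion test to the effectiveness conclusion. But the looseness is limited. Section 1.2 speaks of "Subjects with nasal congestion as determined by the Total Nasal Symptom Score (TNSS", so the plan treats the TNSS as its instrument for congestion, and congestion is one of its four components. Section 2 names the congestion test, so a report that left it out would visibly depart from the plan.

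The case for primary status is weaker. The subscore has no threshold for meaningful change, since 0.28 belongs to the TNSS. It is also the item selected to be high at entry. And the plan is written in the past tense, so promoting it now might have to be reported as a post hoc change.

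**Conclusion.** No change is needed. The mismatch between aim and endpoint is real but partial, and what is missing is the status of an analysis that is already planned. The same data, tests and estimates follow whether or not the label is added. An analyst working from section 2 would report the congestion change beside the TNSS change, and a reader would take any conclusion specific to congestion from that result, allowing for selection on the item and the lack of a control arm.

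The figures of 28 and 112 item falls per 100 subjects, for sum and mean scoring, show only that a TNSS gain without a congestion change is possible. Primary status for the subscore is a design preference with its own costs: up to 5% rather than 2.5% false claims if each measure carries its own claim, under the assumed 95% interval. This conclusion rests on the congestion test being reported as section 2 describes.
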